#### G) Study Relevance and Applicability of Proposed Findings

##### **There is a paucity of information on the impact of SDB and its treatment in chronic SCI.**

Despite the increased prevalence of SDB in SCI, screening for SDB and its treatment are not yet standard of care. To enable change in practice, well-designed RCTs are needed to demonstrate the importance of SDB and its treatment in the health of this population. The following is a summary of perceived knowledge gaps and the beneficial impact of our proposed study:

Aim:	Problem Being Addressed	Beneficial Impact of the Research
1	
Limited data exists on clinically relevant determinants of sleep quality and SDB in persons with SCI. Very little is known about sleep quality and prevalence of sleep disorders in racially diverse persons with SCI.
	
a) The research will quantify sleep quality, mood, pain, and presence of risks for SDB and insomnia in SCI participants using state-of-science evaluation techniques and validated instruments.
 
b) The research brings needed attention to the problem of poor sleep quality and SDB after SCI, particularly among underserved ethnically diverse persons (Hispanic and Black).
 
c) In addition to questionnaires, sleep studies will be conducted using the gold standard of clinical polysomnography, which will provide the most discriminating evidence for diagnosis of SDB.
 
d) A prevalent diagnosis of SDB will justify vigilance from health care providers in anticipating the risk, and provide treatment of this disorder.
 
e) The research will develop a rich database of sleep disorders and clinical outcomes in minorities and underserved SCI participants.

1	
Cognitive deficits in SCI impair rehabilitation and long term social re-adaptation and vocational pursuits. SDB in general, has been associated with impairments in memory, attention, and executive
	
a) The research will identify the association between SDB and cognitive impairments in SCI by using a battery of well-defined neuropsychological tests and comparing

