	
function. These deficits are important for day to day activities.
 
SCI participants with SDB may indeed demonstrate worse cognitive impairment in these domains.
 
More study is needed to determine the full extent of the interaction between SDB and SCI and their combined impact on cognitive function.
	
results between those with and without SDB.
 
b) Additionally, other factors that may impact cognitive performance including pain severity, mood, pre-morbid intelligence, duration of injury, presence of insomnia, and use of sedating medications will be measured and included in a multivariable regression model to better delineate the impact of each of these factors and SDB on cognitive impairment.

1 and 2	
Although there is now some data that demonstrate increased prevalence of poor sleep quality and SDB in SCI subjects, there is no clear evidence that treating these conditions will lead to short and long term benefits.
 
PAP is a medically-justified intervention in persons with SDB, but has seen limited use in persons with SCI. Strength of evidence does not currently support screening for SDB and intervention with PAP in persons with SCI.
 
Persons who are prescribed PAP are not always compliant with its use. Compliance in this population has seen limited study.
 
The impact of PAP on cognitive outcomes in chronic SCI is unknown
 
The impact of PAP on surrogate CV biomarkers, mood, and quality of life in this population is unknown.
	
a) The research will determine the effectiveness of PAP in treating SDB in chronic SCI using gold standard research methodology (RCT).
 
b) The research will provide the empirical support necessary to justify treatment of SDB in persons with SCI.
 
c) The research will examine population-specific compliance levels in PAP use, and identify whether compliance influences health-related outcomes.
 
d) Our clinical trial will identify the impact of PAP therapy on cognitive measures, mood, quality of life, and surrogate CV endpoints. All these measures are relevant to the emotional and physical well-being of participants with chronic SCI and will likely have a practical impact on day to day living in this population.

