### Objectives/Specific Aims/Hypotheses

The proposal describes a multi-center double blinded, placebo controlled randomized trial (RCT) designed to examine the impact of SDB treatment in persons with chronic SCI. The **central hypothesis** is that the treatment of SDB with PAP will improve cognition, sleep quality, HRQOL, and CVD surrogate measures in persons with chronic SCI. The specific aims and hypotheses of the proposed research are:

Specific Aim 1	
Determine the associations between sleep disordered breathing (SDB) and cognitive impairments in chronic SCI and the impact of PAP therapy on cognitive measures in a cohort with chronic SCI and SDB.
 
Hypothesis 1a: Compared with patients without SDB, patients with SDB will exhibit more severe and widespread cognitive impairments (in memory, attention, and executive function), while controlling for depression, pain severity, duration of injury, level of injury, sedative use, and pre-morbid intelligence
 
Hypothesis 1b: SCI participants who are randomized to four months of therapeutic PAP will show improvement in cognitive measures (memory, attention, and executive function) compared with those receiving sham PAP.

Specific Aim 2	
Determine the impact of PAP therapy on surrogate CV biomarkers, sleep quality, quality of life, mood, and pain in a cohort with chronic SCI and SDB.
 
Hypothesis 2a: SCI participants randomized to four months of PAP will show an improvement in CV biomarkers (hs-CRP, TNF-a, VCAM-1, adiponectin, and 8-isoprostanate) compared with sham PAP.
 
Hypothesis 2b: Sleep quality, quality of life, mood, and pain will improve in SCI participants receiving PAP and stay the same or worsen in those randomized to sham PAP.

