## Research Strategy and Study Design

### Study Overview:

During the 4-year study period we will screen 200 SCI participants who meet eligibility criteria and consent to participate with portable level II polysomnography (PSG) and randomize 100 subjects who have SDB to auto-PAP or sham PAP. Participants will be recruited from the University of Miami (Miami Project to Cure Paralysis), the Miami VA, Wayne State University (Michigan Rehabilitation Institute), and affiliated Detroit VA through their outpatient SCI clinics and/or inpatient rehabilitation units. Participants will be asked to complete questionnaires measuring sleep quality (SQ), SDB risk, insomnia severity, daytime sleepiness, pain severity, mood, and HRQOL. They will undergo an overnight, at home (or if hospitalized, in the hospital room) portable unattended PSG performed at their normal sleep time. Subjects with an apnea-hypopnea index (AHI)  $\geq 10$  events/hr will be randomized to receive 4 months of auto-PAP therapy or PAP set at a fixed pressure of 3 cmH20 (sham PAP).

We will perform neuro-psychological evaluations prior to randomization on all participants who complete a portable PSG to evaluate general and pre-morbid function, immediate verbal memory, simple and sustained attention, processing speed, and executive function. Selection of these particular cognitive measures reflects impairments in these domains observed in patients with SDB within the general population. These domains are also impaired in patients with acute and chronic SCI. **Importantly, none of the cited SCI studies have examined the potential role of SDB in cognitive impairment in SCI participants.**

One cognitive measure (PASAT) and 3 sleep questionnaires (PSQI, FOSQ and ESS) will be repeated at 1 month follow-up in those randomized to therapy or placebo. Complete neuro-psychological evaluations will be repeated at the 4 month follow-up time point in those with SDB who were randomized to PAP or sham PAP (primary outcomes). All measures obtained from these repeated assessments will be subject to a Reliable Change Index analysis to control for potential practice effects. We will obtain blood and urine samples for measurement of CV biomarkers at time of randomization and the four month follow-up. Additionally, sleep and quality of life questionnaires will be repeated at four month follow-up (secondary outcomes).

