### ***Sleep Questionnaires***

1) Sleep Quality (SQ): We will assess sleep quality using the Pittsburgh Sleep Quality Index (PSQI). The PSQI is the most widely used global sleep assessment tool. Validity and test-retest reliability of this instrument has been extensively studied. A global PSQI score greater than 5 yields a diagnostic sensitivity of 89.6% and specificity of 86.5% (kappa = 0.75, p < 0.001) in distinguishing 'good' and 'poor' sleepers.

[figure not shown]
2) Chronic Insomnia: We will use the Athens Insomnia Scale (AIS) to assess insomnia in the study population. It consists of eight items: the first five pertain to sleep induction, awakenings during the night, final awakening, total sleep duration, and sleep quality; while the last three items refer to well-being, functioning capacity, and sleepiness during the day. Reliability and validity for the instrument have been well documented.

3) Screening for SDB: We will screen for increased risk of SDB using the Berlin questionnaire (BQ). This is a validated questionnaire with good performance characteristics in the general population. It has been successfully used by our group in the SCI population (see preliminary data).

4) Daytime Sleepiness: Epworth Sleepiness Score (ESS) is a valid measure of subjective daytime sleepiness. Eight items are rated on a scale of 0–3, total scores range 0–24, with higher scores indicating a greater propensity to fall asleep in different situations. In samples of sleep apnea patients, it shows high internal consistency and correlates well with objective measures of sleep latency. It has successfully been used in SCI individuals.

5) Impact of Sleepiness on Functioning: The Functional Outcomes of Sleep Questionnaire (FOSQ) is the gold-standard, disease specific instrument designed to assess the impact of sleepiness on the ability to conduct daily activities. The FOSQ has proven validity and reliability, and is sensitive to treatment changes. There are 30 items, which are divided into 5 scales: Activity, Vigilance, General Productivity, Social Outcome, and Intimacy and Sexual Relationships. These scales are summed to make a total score. Higher scores on the FOSQ indicate self-perceived better daily functioning. The FOSQ has been used by our team in a previous study of acute SCI and sleep disorders.

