**1) Pre-morbid Functioning:**

WIDE RANGE ACHIEVEMENT TEST – IV (READING SUBTEST): The WRAT-IV Reading Subtest is a norm-referenced test that measures the basic academic skill of word reading. It was standardized on a representative national sample of over 3,000 individuals ranging in age from 5 to 94 years. Higher scores are indicative of better sight reading abilities and can serve as a proxy for pre-morbid intellectual functioning.

2) Simple and Divided Attention:

a) DIGIT SPAN SUBTEST OF THE WECHSLER ADULT INTELLIGENCE SCALE –IV: The digit span subtest requires the individual to repeat a series of numbers in the same order, or in reverse order, than orally provided by the test administrator. Low scores on the digit span subtest suggest limited attention, while higher scores indicate a greater ability to concentrate and attend to orally presented information.

b) PACED SERIAL ADDITION TEST (PASAT): The PASAT measures divided, attention and working memory; cognitive domains that have been shown to be particularly salient to SDB. The individual being tested is given single digits at fixed intervals administered by a computer, and needs to add the current number to the last number on each successive presentation. The participant provides verbal responses and the examiner records the responses on a scoring sheet. Lower scores indicate greater impairment of attention.  **The PASAT is the primary outcome measure for this study.**

3) Processing Speed:

SYMBOL DIGIT MODALITIES TEST (SDMT): The SDMT is a substitution task that requires the individual being evaluated to replace symbols with the numbers assigned to them on a reference key. A time limit is imposed to complete the task. Only the oral version of the SDMT will be administered requiring verbal responses. The SDMT has shown excellent reliability, sensitivity, and validity.

4) Memory:

HOPKINS VERBAL LEARNING TEST-REVISED (HVLT-R): The HVLT-R is an assessment of verbal learning and memory, composed of three learning trials, a delayed recall trial, and a delayed recognition trial. It has high test-retest reliability and validity, and has been used in studies of participants with chronic medical conditions. 

5) Executive Function:

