### **Data Analysis:**

Feasibility: The SCI Service at Miami VA actively serves approximately 300 patients. The Miami Project maintains a database of persons who have volunteered their participation in research studies and a database of individuals who have participated in past studies and volunteered additional participation. The database currently contains 3400 persons whose ages and levels of injury match the sought study participants. The Detroit VA SCI service oversees the care of greater than 100 patients/year. The Rehabilitation Institute of Michigan provides care for 350 SCI individuals. We anticipate completion of enrollment by the second quarter of Year 4, with 100 patients enrolled for PSG from each site.

Sample size justification and power: We will recruit 200 participants who meet our eligibility criteria and anticipate an SDB prevalence of 0.50 in SCI participants. This will allow us to randomize 100 participants with SDB to PAP or placebo arm. The neurocognitive test best characterized in both SCI and SDB is the Paced Serial Addition Test (PASAT). The PASAT is our primary study outcome. A mean difference in PASAT scores of 7 discriminates between those with and without cognitive impairment in populations with and without SDB. Assuming a standard deviation of 9 and alpha of 0.05, a sample size of 40 per study arm has a power of 0.93 to detect a mean difference of 7 units. Assuming a PAP non-adherence rate and/or loss to follow-up of 40%, we will continue to have sufficient power (81%) to detect such a difference with our proposed sample size of 100. These findings would be in keeping with PASAT values obtained in non-disabled patients with SDB vs. controls, and PASAT performance in other populations (e.g. multiple sclerosis, mild traumatic brain injury).

Planned analyses: We will score questionnaires while blind to PSG data and group allocation using instructions provided by the questionnaire developer. We will first examine continuous variables for normality. For those variables without a normal distribution, we will explore appropriate transformations in an attempt to achieve normality. Continuous variables will be summarized as means and SD, and categorical variables will be summarized as frequencies. Prevalence of poor SQ will be calculated as the proportion of individuals who complete the PSQI with a score of  $\geq 5$ .

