Prevalence of insomnia will be calculated as the proportion of individuals who complete the AIS with a score  $\geq 6$ . Prevalence of SDB will be calculated as the proportion of individuals who undergo PSG with AHI  $\geq 10/\text{hr}$ .

To determine baseline associations between SDB and cognitive measures (Hypothesis 1a), we will develop Generalized linear models (GLM), with each of the cognitive variables as dependent variables and presence or absence of SDB as an independent variable. The analyses will be repeated with AHI or ODI4 (measures of SDB severity) as independent variables. We will control for other co-variates including age, depression, anxiety, HRQOL, pain severity, duration of injury, level of injury, use of sedating medications, and presence of insomnia. For all GLM developed, the data may be transformed to meet the normality and homogeneity of variance assumptions of the analysis.

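### Two baseline analysis rules do not match the rest of the plan: poor sleep is counted at PSQI 5 or more although accuracy is cited only for scores above 5, and the Hypothesis 1a covariate list leaves out pre-morbid intelligence

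*Combined protocol and SAP*

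**What the plan says.** **PSQI cut-off.** Under Sleep Questionnaires, the plan describes the instrument's ability to separate good from poor sleepers: "A global PSQI score greater than 5 yields a diagnostic sensitivity of 89.6% and specificity of 86.5"%. The planned analyses in the Data Analysis section then set the study's own rule: "Prevalence of poor SQ will be calculated as the proportion of individuals who complete the PSQI with a score of" 5 or more. The PSQI is given no other cut-off or accuracy figure. The study relevance table lists, against Aim 1, that "The research will quantify sleep quality, mood, pain, and presence of risks for SDB and insomnia in SCI participants".

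**Hypothesis 1a covariates.** Under Objectives/Specific Aims/Hypotheses, Hypothesis 1a compares cognition between patients with and without sleep disordered breathing "while controlling for depression, pain severity, duration of injury, level of injury, sedative use, and pre-morbid intelligence". The relevance table makes a similar commitment, saying that factors such as "pre-morbid intelligence, duration of injury, presence of insomnia, and use of sedating medications will be measured and included in a multivariable regression model". The measure is in hand. The Study Overview schedules neuropsychological testing "on all participants who complete a portable PSG to evaluate general and pre-morbid function", and the section on pre-morbid functioning says of WRAT-IV Reading: "Higher scores are indicative of better sight reading abilities and can serve as a proxy for pre-morbid intellectual functioning". The Hypothesis 1a model in the Data Analysis section, however, names as its "co-variates including age, depression, anxiety, HRQOL, pain severity, duration of injury, level of injury, use of sedating medications, and presence of insomnia". Neither pre-morbid intelligence nor WRAT-IV appears there.

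**The concern.** The two points are separate. They are taken together only because both concern baseline analyses in the same section.

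For the PSQI, the plan cites accuracy at one threshold and reports prevalence at another, one score point lower. A reader would naturally attach the quoted sensitivity and specificity to the reported prevalence, and they do not belong to it. At stake is one descriptive figure.

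For Hypothesis 1a, the adjustment set is part of the hypothesis. The operative model adds two covariates that neither commitment names (age and health-related quality of life) and omits one that both name. An analyst who fits what is listed would test a different hypothesis in every cognitive model, including the repeats with AHI and ODI4 in place of the SDB indicator. Leaving the choice until the data are seen also leaves discretion over the adjustment set of a numbered hypothesis.

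**Working it through.** **1. PSQI**

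The plan states no expected prevalence of poor sleep, so there is no figure to reproduce.

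The PSQI score is a whole number, so the two rules differ only for people scoring exactly 5:

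- prevalence at 5 or more = prevalence above 5 + share scoring exactly 5.

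The direction is therefore fixed: the planned rule cannot give a lower prevalence. For the same reason, in the samples behind the cited accuracy, sensitivity at 5 or more is at least 89.6% and specificity at most 86.5%.

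The size depends on the number scoring exactly 5, which the documents do not give. Take n = 200 (the planned recruitment) and assume that all complete the PSQI:

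- Shift per person = 1/200 = 0.5 percentage points, so 2 people move the prevalence by 1 point.
- For scale, the 95% sampling half-width of a prevalence p is 1.96 × √(p(1 − p)/n).
- At an assumed p = 0.50: 1.96 × √(0.25/200) = 0.0693, or 6.9 points. 0.0693 × 200 = 13.9, so the shift exceeds the half-width from 14 people upward.
- At an assumed p = 0.80: 1.96 × √(0.16/200) = 0.0554, or 5.5 points. 0.0554 × 200 = 11.1, so it does so from 12 people upward.
- As an illustration only, if 3% to 15% of participants score exactly 5, then 6 to 30 people are reclassified and the prevalence rises by 3 to 15 points.

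Below 14 or 12 people the shift is smaller than sampling error, but it is always upward.

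**2. Hypothesis 1a covariates**

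The three lists side by side:

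| Factor | Hypothesis 1a | Relevance table | Data Analysis model |
|---|---|---|---|
| Depression | yes | yes (as mood) | yes |
| Anxiety | no | within mood | yes |
| Pain severity | yes | yes | yes |
| Duration of injury | yes | yes | yes |
| Level of injury | yes | no | yes |
| Sedating medication | yes | yes | yes |
| Insomnia | no | yes | yes |
| Age | no | no | yes |
| Health-related quality of life | no | no | yes |
| Pre-morbid intelligence | **yes** | **yes** | **no** |

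Hypothesis 1a names 6 factors, of which the model names 5. The relevance table names 6 (counting mood as one), of which the model covers 5. The model names 9 in all. The single missing item is the same in both comparisons.

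Nothing in the model stands in for it. Years of education is named as a covariate only for the PASAT treatment comparison (Hypothesis 1b). There is a further ambiguity: the Hypothesis 1a models take each cognitive variable as an outcome, and WRAT-IV is the first test in the cognitive battery. Read literally, the plan could have it modelled as an outcome when its stated purpose is to stand for pre-morbid ability.

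The documents give no correlations from which to derive the bias or the loss of precision, so none is estimated.

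**The case against.** On the covariates, the best reply is that this is one combined document. Hypothesis 1a already specifies the adjustment, the relevance table repeats it, and the model's list is introduced with the word *including*, so nothing is ruled out. A careful analyst would read the sections together and include WRAT-IV. That is fair, and it is why the point is an omission and not a contradiction. It does not remove the need for the change: the Data Analysis section is what an analyst will program from, and it names additions that nobody promised while leaving out an item promised twice.

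On the PSQI, no two study rules conflict. The accuracy statement describes the instrument, and the only operational definition is 5 or more. The insomnia cut-off (AIS of 6 or more) likewise has no accuracy figure, the plan does not say that the PSQI figures come from people with spinal cord injury, and citing support for 5 or more would also settle the matter. All of this stands. The PSQI differs from the AIS in that the plan does cite an accuracy, and at an adjacent threshold. The instruction to score by the developer's rules does not resolve it, because the same paragraph then sets its own cut-off.

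It is also true that sleep quality is not in the wording of Specific Aim 1, only in the relevance table, and that no hypothesis test is said to use the poor-sleeper classification. The prevalence can be recomputed from stored scores. These facts limit the weight of the point.

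**Conclusion.** Both mismatches hold, and both are minor.

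The PSQI rule reports prevalence at a cut-off for which the plan offers no support, and it can only raise the figure relative to the cited cut-off. The amount is unknown. The threshold counts of 14 and 12 people rest on 200 completed questionnaires and on assumed prevalences of 50% and 80%; they show when the shift would matter, not that it will.

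The Hypothesis 1a model leaves unnamed one of the six covariates written into the hypothesis. No size of bias is claimed. The covariate point is the better supported of the two, since the plan makes the commitment explicitly in two places.

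The primary PASAT comparison and the sample size are unaffected.

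**What to change.** Make two edits to the planned analyses in the Data Analysis section, before the data are analysed:

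1. Define poor sleep quality as a PSQI global score greater than 5, the cut-off whose accuracy the plan cites. If 5 or more is intended, the plan needs to cite support for that threshold.
2. Add WRAT-IV Reading, as the proxy for pre-morbid intelligence, to the named covariates for Hypothesis 1a, and state that it enters as an adjuster and not as an outcome.

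The cost is wording only, plus one extra term in each Hypothesis 1a model. Both measures are already scheduled at baseline, WRAT-IV for everyone who completes polysomnography, so there is no new data collection, added participant burden or change in sample size.
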